2. SYNOPSIS

Trial Title	Investigation of Appropriate Timing of Additional Insulin Dosing for Fat and Protein in Children with Type 1 Diabetes using Multiple Daily Injections	
Internal ref. no. (or short title)	Fat/Protein Study	
Clinical Phase	Phase 4	
Trial Design	Controlled observational study	
Trial Participants	Children aged 6 to under 18 years of age with type 1 diabetes (T1DM)	
Planned Sample Size	40	
Treatment duration	1 week	
Follow up duration	No follow-up at the end of the trial period	
Planned Trial Period	1 year	
	Objectives	Outcome Measures
Primary	To determine whether additional insulin boluses for the fat and protein content of a meal given before, one or two hours after a meal optimise post-prandial blood glucose levels in children with Type 1 diabetes using multiple daily injections?	Continuous subcutaneous glucose profiles will be examined to determine – 
 • mean post-prandial glucose excursion for 8 hours following the test meal
Secondary	To examine other indices of BG control following additional insulin boluses for the fat and protein content of a meal given before, one or two hours after a meal in children with Type 1 diabetes using multiple daily injections?	Continuous subcutaneous glucose profiles will be examined to determine – 
 • peak BG level • peak BG excursion from baseline (pre-meal BG level) • time of peak BG level from baseline measurement • Rate of BG excursion from baseline to peak • mean post-prandial glucose excursion for 5 and 12 hours following the test meal • area under the curve at time-points 0-3 hours, 3-5 hours, 5-8 hours, 8-12 hours post-meal • Time from baseline BG at which BG returns to baseline level
Investigational Medicinal Product(s)	Insulin	
Formulation, Dose, Route of Administration	Insulin Aspart (NovoRapid) given in a dose according to the protocol, subcutaneously	

3. ABBREVIATIONS

AE	Adverse event
AR	Adverse reaction
BG	Blood Glucose
CGM	Continuous subcutaneous glucose monitor
CHO	Carbohydrate
CI	Chief Investigator
CRF	Case Report Form
CT	Clinical Trials
CTA	Clinical Trials Authorisation
DMC/DMSC	Data Monitoring Committee / Data Monitoring and Safety Committee
DSUR	Development Safety Update Report
GCP	Good Clinical Practice
GP	General Practitioner
ICF	Informed Consent Form
ICH	International Conference on Harmonisation
ICR	Insulin to carbohydrate ratio
IMP	Investigational Medicinal Product
IRB	Independent Review Board
MDI	Multiple Daily Injections
MHRA	Medicines and Healthcare products Regulatory Agency
NHS	National Health Service
NRES	National Research Ethics Service
PI	Principal Investigator
PIL	Participant/ Patient Information Leaflet
R&D	NHS Trust R&D Department
REC	Research Ethics Committee
SAE	Serious Adverse Event
SAR	Serious Adverse Reaction
SDV	Source Data Verification
SMPC	Summary of Medicinal Product Characteristics
SOP	Standard Operating Procedure
SUSAR	Suspected Unexpected Serious Adverse Reactions

TMF	Trial Master File
TSG	Oxford University Hospitals Trust / University of Oxford Trials Safety Group

4. BACKGROUND AND RATIONALE

Type 1 Diabetes incidence in children is increasing in the UK and internationally. Blood glucose (BG) control is improved with intensive insulin therapy including multiple daily injections and insulin pump therapy, and long-term complications are known to be related to blood glucose control [1]. Post-prandial BG levels have been linked with the risk of cardiovascular disease, one of the major complications of diabetes [2].

In order to keep BG levels as normal as possible, all children in our clinic on intensive insulin management are taught to match insulin dose to the carbohydrate quantity in food. We and others have previously demonstrated that children and their families can learn to count the quantity of carbohydrate in food [3], and that the link between carbohydrate quantity and insulin dose does affect the post-prandial BG level [4].

There is increasing evidence that the fat and protein content of food affects BG levels in addition to the known effect of the carbohydrate content of the food. Pankowska's group were the first to routinely count fat and protein in food, and to use this value to calculate additional insulin doses given as prolonged boluses in children using insulin pumps to maintain good BG control, demonstrating that those children who used such doses and boluses were more likely to achieve target levels of control [5]. Subsequent studies by the same group and others have refined the technique to demonstrate improved PPBG levels in children using insulin pumps [6,7].

A recent study by Smart et al has shown that the post-prandial BG levels can remain high for several hours after high fat and high protein meals when insulin is given purely for the carbohydrate content [8]. Furthermore, the effect is additive, with high protein and high fat meals causing high post-prandial BG levels which had not returned to pre-prandial levels up to 6 hours after a meal [8].

A recent systemic review of ten studies examining insulin bolus dose and delivery patterns required for high fat and/or high protein meals has generated recommendations for clinical practice [9]. Although all the studies included have been conducted in patients using insulin pumps (adults and children) the authors have extrapolated their conclusions to make recommendations for changes to insulin dose calculations and delivery options in both CSII and MDI therapy.

It is suggested that for high fat meals containing over 40g fat that insulin doses should initially be increased by 30-35% on the usual dose calculated using their ICR with the extra insulin given as a separate injection 1 hr after the meal. This dose should be monitored and increased according to individual response [9].

They also recommend that for meals containing 30g fat and 40g protein that the insulin dose calculated with usual insulin:carbohydrate ratios should be increased by 15-20% but do not suggest a delivery method for this extra insulin [9]. It should be noted that all these recommendations are intended for an adult population.

The review recognises gaps in knowledge and evidence base to support specific recommendations and algorithms to calculate insulin doses and delivery patterns according to the fat and protein content of meals. Furthermore, they identified significant inter-individual variability in post-prandial glycaemic response to high fat and protein meals which may be a confounding factor to research and meaningful conclusions in this area [9].

We therefore plan to investigate how to appropriately administer additional insulin for the fat and protein content of high protein and high fat meals to children on multiple daily injections (MDI) to improve BG levels up to 12 hours after a meal.

In line with our previous studies (3,4) and as indicated from a power calculation, we will recruit forty patients from the Oxfordshire Children's Diabetes Service aged from 6 to under 18 years and obtain full informed consent. There will be a run-in period of 7 days during which time the children's insulin to carbohydrate ratios will be optimised.

The children will then be asked to wear continuous subcutaneous glucose monitors (CGM) which are a well-recognised and validated method of monitoring BG levels over several days. The particular version we will use for this study lasts for 7 days.

During the 7 day study period, the children will be asked to consume a standard high-fat, high-protein test meal on 3 separate evenings. They will be asked to give insulin for the carbohydrate (CHO) content of the meal before the meal on all 3 days. Additional insulin will be calculated for the fat and protein content on the basis of the Pankowska equation [6] and recommendations from the most recent systemic review of current research [9] and will be given in a random order, either before, 1 hour after, or 2 hours after the first insulin dose before meal. The child and family will be able to choose which days during the study period on which they complete the study meals but will be advised to avoid the day that the CGM sensor was inserted, days when the participant has undertaken lots of exercise, is hypoglycaemic immediately before the meal, or has had frequent hypoglycaemic episodes earlier in the day or has been unwell.

BG levels will be monitored using the CGM for the evening and overnight until the next morning.

5. OBJECTIVES AND OUTCOME MEASURES

Objectives	Outcome Measures	Timepoint(s) of evaluation of this outcome measure (if applicable)

Primary Objective To determine whether additional insulin boluses for the fat and protein content of a meal given before, one or two hours after a meal optimise post-prandial blood glucose levels in children with Type 1 diabetes using multiple daily
	
Continuous subcutaneous glucose profiles will be examined to determine –
 
 mean post-prandial glucose excursion for 8 hours following the test meal 	
Continuous Glucose Monitoring profiles during the 12 hours following the test meals

[figure not shown]
injections?		

Secondary Objectives
 
To examine other indices of BG control following additional insulin boluses for the fat and protein content of a meal given before, one or two hours after a meal in children with Type 1 diabetes using multiple daily injections?
	
Continuous subcutaneous glucose profiles will be examined to determine –
 
 • peak BG level • peak BG excursion from baseline (pre-meal BG level) • time of peak BG level • timing of peak BG excursion 
area under the curve at time-points 0-3 hours, 3-5 hours, 5-8 hours, 8-12 hours post-meal
	
Continuous Glucose Monitoring profiles during the 12 hours following the test meals

Tertiary Objectives
 
1. To assess the acceptability of giving additional insulin doses for fat and protein to children using MDI
 
2. To assess the safety of giving additional insulin doses for fat and protein to children using MDI
	
1. Questionnaires to parents and children during and at the end of the study
 
2. All episodes of hypoglycaemia (BG less than 4 mmol/l) or hyperglycaemia (BG >12 mmol/l) either on CGM or self-monitoring of BG
	
Collection of data during and at the end of the study

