11.1. Description of Statistical Methods

Descriptive statistics will be used to describe the group demographics and outcomes.

The continuous glucose records will be analysed methodically by the CI, research dietitian and statistician. Data to be obtained include –

- pre-meal BG level
- peak BG level
- peak BG excursion from baseline at 3, 5, 8 and 12 hours following the meal
- time of peak BG level
- time of peak BG excursion
- area under the curve at time-points 0-4 hours, 4-6 hours, 6-8 hours, 8-12 hours post-meal

The relationship between the insulin timing and the mean change in postprandial blood glucose levels will be analysed and described.

Comparisons using paired t tests for normally distributed data, and Mann-Whitney U tests for non-parametric data will be used to examine the differences in areas under the postprandial BG curves and the postprandial BG levels by insulin timing.

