11.6. Inclusion in Analysis

All data available from all participants will be used for the analyses. If a child has become hypoglycaemic (BG $< 4.0 \text{ mmol/l}$) during the profile period then subsequent data will be analysed separately. If any child has had to treat a high BG level with additional insulin (except for a correction dose at the evening meal), then subsequent profile data will be analysed separately. However in either instance, the data up to the event will be included in all analyses. The two other meals would still be eligible for the study analyses if there were no similar events.

If there have been any protocol breaches, such as further food during the evening after the main meal, then all the subsequent data will not be used in the analysis for that meal. Education of the participants and parents will be vital to ensure that such eventualities are rare.

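### Hypoglycaemia is not compared between the three insulin timings, and the 8-hour mean excursion is cut short at a low, which may itself differ by timing

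*Combined protocol and SAP*

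**What the plan says.** The primary measure (Synopsis and Section 5) is "mean post-prandial glucose excursion for 8 hours following the test meal". The secondary measures are peaks, their timing, further mean excursions and areas under the curve. None is a nadir, time below 4 mmol/l or a frequency of lows.

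Hypoglycaemia appears under the second tertiary objective in Section 5, "To assess the safety of giving additional insulin doses for fat and protein to children using MDI", with the measure "All episodes of hypoglycaemia (BG less than 4 mmol/l) or hyperglycaemia" (above 12 mmol/l for the latter). Section 6.3 shows that all three conditions receive the extra dose and that only its timing differs.

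Section 11.1 does not list hypoglycaemia among the data to be obtained. Its tests are to "examine the differences in areas under the postprandial BG curves and the postprandial BG levels by insulin timing". It also has a general sentence: "Descriptive statistics will be used to describe the group demographics and outcomes".

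If a child goes below 4.0 mmol/l "during the profile period then subsequent data will be analysed separately" (Section 11.6). That section adds: "However in either instance, the data up to the event will be included in all analyses". Under Section 6.3, a second study dose still due after a low is omitted. Section 11.4 stops the trial after two severe episodes on any arm. Section 11.5 plans a complete-case analysis, with multiple imputation as a sensitivity analysis.

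**The concern.** Two gaps bear on the same question.

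First, the trial is about timing, but its safety objective is about extra insulin as such. Because every condition includes the extra dose, episodes pooled over conditions cannot show whether one timing produces more lows than another. The sponsor already treats lows as a live issue: Appendix B records that Amendment 2 reduced the extra insulin in order to lower that risk.

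Second, the rule in Section 11.6 cuts the primary measure at an outcome of treatment. If lows are more frequent, or come at a different time, under one timing, the retained 8-hour means no longer cover the same hours in each condition. A difference between timings could then partly reflect where profiles were cut. The plan does not say how a cut profile enters an 8-hour mean, what the separate analysis consists of, or whether values set aside count as missing for Section 11.5.

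**Working it through.** **1. The plan's own arm-specific figure.** The only hypoglycaemia figures by arm are those of the stopping rule. Section 11.4 gives 10 severe episodes in 340 patients per year: 10/340/365 = 0.0000806 per child-day. With 40 children and one day per condition, the expected number per timing is 40 × 0.0000806 = 0.0032. The chance of at least one episode over three conditions is 1 - (1 - 0.0000806)^120 = 0.96%, in line with the plan's figure of about 1 in 100. (Its 3 in 10,000 for two episodes does not follow from that exposure, which is a separate matter.) So few events cannot distinguish the timings, and the rule does not cover BG below 4 mmol/l.

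**2. Effect of the cut on one meal.** Let a low occur at T hours, with mean excursion m1 before it and m2 after it.

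- Full 8-hour mean = [T × m1 + (8 - T) × m2]/8
- Retained mean = m1
- Retained minus full = [(8 - T)/8] × (m1 - m2)

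The sign is that of m1 - m2, so the direction depends on when the low occurs. The profiles below are assumptions; the documents give none.

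- *Early low, then rebound.* Baseline 8 mmol/l, low at 115 min (T = 1.917 h), m1 = -1.63, full mean +1.82. Then m2 = [8 × 1.82 - 1.917 × (-1.63)]/6.083 = +2.91, and the shift is (6.083/8) × (-1.63 - 2.91) = -3.45. The meal looks better. A comparable meal without a low has +1.80, almost the same as the full trace of the meal with one.
- *Low after a sustained high.* T = 4, m1 = +3.0, m2 = +0.5. The shift is 0.5 × 2.5 = +1.25. The meal looks worse.

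**3. Effect on a comparison of timings.** If a share p of meals at one timing is cut with average shift d, that timing's mean moves by p × d. Suppose the shares differ by 10 percentage points and d is the same in both timings. With d = -3.45, the contrast moves by 0.10 × 3.45 = 0.35 mmol/l; with d = +1.25, it moves by 0.13 mmol/l the other way. For a 30-point difference the figures are 1.04 and 0.38. For scale, Section 11.2 is powered for 2 mmol/l (on the 5-hour excursion).

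A simulation with assumed profiles, mostly of the early-low kind in timing A, gave these mean excursions in mmol/l:

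| Handling of meals with a low | Timing A (17.8% low) | Timing B (4.7% low) | A - B |
|---|---|---|---|
| Full trace | 1.66 | 1.46 | +0.20 |
| Cut at the low | 1.05 | 1.42 | -0.37 |
| Meal dropped | 1.50 | 1.51 | -0.01 |

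The ranking depends on a choice that the plan leaves open. This shows that a reversal is possible, not that it is likely.

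**4. What the planned data can support.** For the share of meals with a low at two timings, assuming independence within child, the 95% half-width is 1.96 × √{[p1(1 - p1) + p2(1 - p2)]/n}. With n = 40:

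- 10% v 20%: 1.96 × √(0.25/40) = 15 points
- 20% v 40%: 1.96 × √(0.40/40) = 20 points

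Exact McNemar power at n = 36 and n = 40 (assumed rates) is 13% and 15% for 10% v 20%, 36% and 40% for 20% v 40%, and 79% and 84% for 10% v 40%.

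**The case against.** The best defence is that hypoglycaemia is far from ignored. It is a named outcome, Section 11.1 promises descriptive statistics on outcomes, Section 10.3 keeps mild lows in the diary and CGM record, and data after a low are analysed separately rather than discarded. A table by timing could be produced from all this. That stands, and a reader who inferred that no planned result could reveal an excess of lows would go too far. What remains is that neither hypoglycaemia nor a split by timing is named in the analysis.

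Three other stronger readings are tempting, and the documents do not support them:

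- *That late lows cancel early highs in the primary mean.* Under Section 11.6, values after the low leave that analysis. A profile that is high and then low keeps mainly its high part and looks worse.
- *That the cut always favours the timing with more lows.* Step 2 shows both directions.
- *That the plan will call a timing optimal on mean excursion alone.* There is no such rule. Section 11.1 says only that the relationship will be analysed and described, and peaks and areas are examined too.

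It can also be objected that the full trace after a low is not clean. It includes treatment of the low and, in the 1-hour and 2-hour conditions only, possible omission of the second dose. That is correct, and it is why both versions should be shown.

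**Conclusion.** The point holds in a limited form. Section 11 plans no comparison of BG below 4 mmol/l between timings, and Section 11.6 truncates the primary measure at an event that may depend on timing, without saying how truncated profiles enter the 8-hour mean. Both follow from the text and need no assumption.

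The size and direction of any bias are unknown, because the documents give neither rates of low BG by timing nor profiles. Under the assumed shifts, a 10-point difference in the share of cut meals moves the contrast by about 0.1 to 0.35 mmol/l. That is small beside 2 mmol/l, but enough to change a close ranking. The sponsor should settle this before analysis; it does not invalidate the design.

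**What to change.** Add to Section 11:

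1. By timing, beside the primary result and using the full CGM trace: the proportion of meals with any BG below 4.0 mmol/l within 8 h and within 12 h, and the percentage of the 8 h below 4, from 4 to 12, and above 12 mmol/l (the protocol's own cut-offs). Give within-child paired differences with 95% confidence intervals.
2. Mean 8-hour excursion by timing, both on the full trace and on data cut at a low, with a definition of how a cut profile contributes. Report by timing how many meals were cut and how many second doses were omitted.
3. A statement that mean excursion will be interpreted together with these hypoglycaemia results.

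The cost is analysis wording only, since CGM values are already recorded every 5 minutes. There are two downsides. The hypoglycaemia results will be imprecise estimates, not powered tests. Full-trace values after a low also reflect its treatment and, in the two delayed conditions, possible omission of a dose, so they must be labelled as such.

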6. TRIAL DESIGN

6.1. Summary –

The study design is a repeated measures study involving the provision of a standard high protein/high fat evening test meal on 3 different evenings within a 7-day period in the same study subject. The children/adolescents will be instructed to give an insulin dose for the carbohydrate before the meal (calculated using their optimal insulin to carbohydrate ratio (ICR)). In addition they will have an extra dose for the fat and protein content either before (together with the dose for the carbohydrate in the meal [control meal]), 1 hour after, or 2 hours after the first insulin dose given before the meal. These will be carried out in a random order in each subject. Glucose monitoring will be carried out using CGM for the whole 7 day period.

6.2. Study Flow Chart -

6.3. Detail –

The clinical diabetes team in each participating hospital will identify children in the service who are using multiple daily injections to manage their diabetes and who would be eligible for the study. In addition, in Oxford, an e-mail will be sent to all patients signed up to the e-mail service to alert them that the study is open to recruitment. The study will also be advertised in the Oxford 3 monthly newsletter and families could volunteer if they are interested in their children taking part. There will also be a poster made for both the Oxford and Reading clinics to advertise the study. Once the family has expressed an interest in hearing more about the study, the relevant information sheets will be handed to the patients in clinic or sent by post.

After the initial contact, the research nurse or dietitian will telephone the patient and family after a week to answer any questions they may have about the study. If they are keen to participate, an appointment will be arranged for consent and to commence the study (Visit 1). If the patient or family do not wish to take part at this point this would be documented on the approach log.

At Visit 1 we will obtain informed consent (see section 7.2) and commence a week-long run-in period for participants to optimise insulin to carbohydrate ratio at the evening meal. During this week subjects will be requested to test BG levels at 7 points throughout the day (pre-meals, 2 hrs after meals and bed). They will be asked to eat a fat and protein free meal on one of these days. If necessary, adjustments to the insulin to carbohydrate ratio (ICR) or long-acting insulin doses will be made over the telephone or via email by an experienced member of their clinical team. This is to decrease the likelihood of a high or low BG level at the evening meal during the study week which would require the meal to be abandoned.

At the end of the run-in week, participants will then attend the outpatient clinic or day care ward research facility at the Oxford Children's Hospital or the Horton Hospital outpatient clinic in Banbury or the Royal Berkshire Hospital in Reading (Visit 2). At this visit, the subcutaneous glucose sensor will be inserted by the research nurse and children and young people and their families will be trained on its use prior to the study commencing. CGM records BG levels every 5 minutes over 7 days and thus provides much more information than routine BG testing. These systems are regularly used by the Paediatric Diabetes team in clinical care and are well accepted by patients. The CGM records will enable researchers to calculate the area under the curve for post-prandial BG response to determine if there are significant differences between the test insulin dosing schedules. Children and young people will also record their BG levels from routine finger pricks, pre-prandially and before bed and on waking in the morning.

We considered using a blinded CGM system which does not reveal current blood glucose levels in order to reduce participant and parental anxiety, however the only system like this on the market does not alarm on hypoglycaemia which is an essential safety measure for this study and this option was therefore rejected.

Also at Visit 2, the study dietitian will review BG readings and food diary from the previous week and optimise ICR doses of rapid acting insulin. This ratio will then be used to calculate insulin doses for the study meals according to the following algorithm based on the Pankowska (Warsaw) equation [6] and recommendations from the latest systemic review of current research [9]

Insulin dose for carbohydrate = g CHO x ICR

Insulin dose for fat and protein = FPU x (0.3 x ICR)

TOTAL Insulin dose = (g carbs x ICR) + (FPU x (0.3 x ICR))

Where FPU = fat-protein unit and 1 FPU = 100kcal from fat and protein

On three evenings over the next 7 days, the children will eat a standard high protein/high fat meal. The evenings will not be set, but will depend on the child and family schedule. The study meal will not be eaten on the evening that the CGM is inserted as sensor accuracy takes 24 hours to maximise accuracy. The child and family will be able to choose which days during the study period on which they complete the study meals but will be advised to avoid days when the participant has undertaken lots of exercise, is hypoglycaemic immediately before the meal or has had frequent hypoglycaemic episodes, or has been unwell.

The standard meal will be a portion controlled gluten-free meal provided and delivered by Wiltshire Farm Foods consisting of a meat-based main course and dessert. These will be kept frozen until used by participants and prepared according to manufacturer instructions. These meals come in two sizes which allow portion sizes to be adjusted for different ages of child, but the proportions of fat, protein and carbohydrate will be kept constant for each child, and by definition the meals will be high in protein and high in fat.

Insulin doses with the standard meal will be given according to calculations carried out by the dietitian and administered in one of three ways.

The three evenings in random order will be as follows -

1. Insulin units based on ICR and fat/protein dose given together immediately before the meal [control meal].
2. Insulin units based on ICR given immediately before the meal plus extra insulin for fat/protein units given 1 hour after the first meal dose.
3. Insulin units based on ICR given immediately before the meal plus extra insulin for fat/protein units given 2 hours after the first meal dose.

Participants will be asked not to give a correction dose before the meal if the BG level is between 7-12mmol/l as this would interfere with the analysis. They will be asked, if possible, not to carry out the test meals if their pre-meal BG is greater than 12 mmol/l. But if they have to do the test meal with a high pre-meal BG (above 12 mmol/l) they will be instructed to give their usual correction bolus in addition to the prescribed insulin dose for the test meal. This data will be analysed separately. If BG is below 4mmol/l (hypoglycaemic) or above 16mmol/l participants will be asked to abandon the study evening and repeat on another evening. Full written instructions will be provided to the family for all aspects of the insulin dosing for the study meals.

During the study on the standardised meal days children will be instructed not to eat any food after the meal during the evening, and not to correct any later BG levels unless they are dangerously high (BG over 16 mmol/l with ketones over 0.5 mmol/l). If BG levels go low at any time (BG less than 4 mmol/l) children will be instructed to treat the hypoglycaemia according to their usual management, and omit

any further study doses of insulin if the hypoglycaemia occurs after a first study dose and a second is due. This data will be analysed separately. Children and families will be asked to complete diaries during the trial week.

At the end of the study period (the day after the third meal), children will come back to the research facility or clinic for the end of study visit (visit 3). A research nurse or dietitian will remove the CGM sensor and download the data onto a secure laptop. Children and their families will then be asked to complete a short questionnaire about the acceptability of using the extra insulin doses, and their perceptions as to whether there were any beneficial or adverse effects.

The study dietitian will calculate standard outcomes from each patient's sensor download and pass on anonymously to the study statistician to analyse the data.

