8.5. Subsequent Visits

Visit 2 – Study visit

- A review of the BG levels in the preceding week will be carried out by the study dietitian, in order to determine whether any further adjustments in insulin dose need to be made.
- The CGM will be inserted.
- Randomisation of the insulin dose order will be carried out and final dose calculations will be done by the dietitian according to the equations in section 5.3.
- Full written instructions will be provided to the participants, including insulin doses and timings for the three study meals, contact details and what to do if BG levels should be high (greater than 16mmol/L) or low (less than 4mmol/L).
- There will also be instructions about what they should do in the event of a sensor malfunction.
- The child and family will be informed that they can call the research team during office hours at any stage to discuss events during the week of the study, and they will be provided with contact details. If any advice is required outside office hours, they will be advised to contact their clinical diabetes team in the usual way.

Visit 3: End of study visit - The participant will return to their original outpatient or day-care setting and the CGM sensor will be removed by the study nurse and data downloaded onto the web-based system Diasend which is regularly used in clinics. Participants and their family will have the opportunity of viewing the download from the sensor. The participant and parent will be asked to complete the short questionnaires about the acceptability of the additional insulin doses.

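### The Section 6.3 dose formula applies one insulin-to-carbohydrate ratio to grams and to 100-kcal units with no conversion, so 100 kcal of fat and protein is dosed as 0.3 g of carbohydrate

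*Combined protocol and SAP*

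**What the plan says.** Section 6.3 (Detail) gives the algorithm in three lines and a definition. Closing brackets fall outside the quotations.

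- Carbohydrate: "Insulin dose for carbohydrate = g CHO x ICR".
- Fat and protein: "Insulin dose for fat and protein = FPU x (0.3 x ICR".
- Total: "TOTAL Insulin dose = (g carbs x ICR) + (FPU x (0.3 x ICR".
- Definition: "Where FPU = fat-protein unit and 1 FPU = 100kcal from fat and protein".

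The text introducing these lines bases them on the Warsaw equation (reference 6) and a systematic review (reference 9), and says that the single ratio optimised in the run-in is used for the study meals. The abbreviations list expands ICR but gives it no unit.

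Section 4 reports that review as advising, for "meals containing 30g fat and 40g protein that the insulin dose calculated with usual insulin:carbohydrate ratios should be increased by 15-20" per cent, and notes that its recommendations are meant for adults. Amendment 2 in Appendix B says that the calculation was changed to give less insulin for fat and protein and so lower the risk of hypoglycaemia; it does not show the formula it replaced.

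On the meal, Section 6.3 says "These meals come in two sizes which allow portion sizes to be adjusted for different ages of child", without the macronutrient content of either size. For Visit 2, Section 8.5 says "final dose calculations will be done by the dietitian according to the equations in section 5.3".

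**The concern.** ICR is a ratio of insulin to carbohydrate. It can multiply a quantity of carbohydrate, but not a count of 100-kcal units until that count is expressed as carbohydrate. The formula omits that step, and the total line repeats the omission.

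The timing of this extra dose is the only thing that differs between the three evenings, so its size determines what is being compared. There are two possibilities:

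- **A conversion was used that is not printed.** This is the likelier case. A change made to reduce hypoglycaemia, and the Section 6.3 instruction to omit a pending second dose after a low reading, both suggest a dose large enough to matter. This is inference, because the replaced formula is not shown. If so, the insulin given to children is not the dose the protocol specifies. Section 9.3 allows data to be removed when the advised dose was not given, yet that advised dose cannot be checked against the protocol.
- **The line was followed as printed.** For meals of the kind worked through below, the evenings would then differ only in when a fraction of a unit was injected.

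**Working it through.** The documents give no worked dose, no meal composition and no numeric ICR, so there is no stated figure to reproduce. The first two steps need only the printed formula; the later ones use labelled assumptions.

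**1. Carbohydrate equivalent of one FPU.** Set the dose for one FPU equal to the dose for *x* grams of carbohydrate:

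0.3 × ICR = *x* × ICR, so *x* = 0.3 g.

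**2. Extra dose relative to the carbohydrate dose.**

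(FPU × 0.3 × ICR) / (g CHO × ICR) = 0.3 × FPU / g CHO.

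ICR cancels, so no unit for it repairs the rule:

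- Units of insulin per gram: the carbohydrate line is right, and one FPU counts as 0.3 g.
- Units per 10 g: the fat/protein line grows, but the carbohydrate dose becomes ten times too high.
- Grams per unit: multiplying is wrong in both lines.

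**3. The Section 4 meal.** Assumptions: 9 kcal/g for fat, 4 kcal/g for protein.

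- (30 × 9 + 40 × 4) / 100 = 430 / 100 = 4.3 FPU.
- Carbohydrate equivalent as printed: 0.3 × 4.3 = 1.29 g.

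A larger assumed meal of 8 FPU gives 0.3 × 8 = 2.4 g. The trial meal's carbohydrate content is not given, so a range is shown.

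| Assumed CHO | Extra dose, 4.3 FPU | Extra dose, 8 FPU |
|---|---|---|
| 30 g | 1.29/30 = 4.3% | 2.4/30 = 8% |
| 60 g | 1.29/60 = 2.2% | 2.4/60 = 4% |
| 80 g | 1.29/80 = 1.6% | 2.4/80 = 3% |

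**4. In units of insulin.** At an assumed ICR of 0.05 to 0.2 U per g:

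- 4.3 FPU: 1.29 × 0.05 = 0.06 U to 1.29 × 0.2 = 0.26 U.
- 8 FPU: 2.4 × 0.05 = 0.12 U to 2.4 × 0.2 = 0.48 U.

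**5. Comparison with the 15-20% in Section 4.** For the 4.3 FPU meal the printed rule reaches 15% only at 1.29 / 0.15 = 8.6 g of carbohydrate or less, and 20% only at 1.29 / 0.20 = 6.45 g or less. In general the result is below 15% whenever g CHO > 0.3 × FPU / 0.15 = 2 × FPU. At an assumed 4 kcal/g for carbohydrate, that is any meal with more than 8 / 108 = 7.4% of its energy from carbohydrate.

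**6. How large the missing factor could be.** Let *k* be the grams of carbohydrate assigned to one FPU before the 0.3 multiplier; the printed line amounts to *k* = 1. For the 4.3 FPU meal, reaching 15-20% needs *k* = (0.15 to 0.20) × g CHO / 1.29. That is 3.5 to 4.7 at an assumed 30 g of carbohydrate and 11.6 to 15.5 at 100 g. This shows how far the dose depends on an unstated number; it does not propose a value.

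**The case against.** The strongest reply is that this is a documentation gap that does not threaten validity. Families do not calculate anything: the dietitian works out the doses and supplies written instructions, one research team covers all sites, and Section 9.3 requires a diary of the doses actually given. The same extra dose applies on all three evenings, so the within-child timing comparison is not biased by its size alone. Literal use would err towards too little insulin, not towards hypoglycaemia. The cited Warsaw equation may also supply the conversion.

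Much of this stands. The doses given should be recoverable from trial records, nothing shows that any child was under-dosed, and no bias in the comparison is claimed. But diaries record what was injected and do not repair the rule. The protocol says only that its algorithm is based on the cited sources; it then prints its own version, in a calculation that amendment 2 changed. The printed lines are the only statement of the current dose.

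Two supporting points carry less weight. The 15-20% figure is tied to one adult meal, and a smaller dose in children could be deliberate, so the general 15% threshold in step 5 is a yardstick and proves no error. The Visit 2 reference to Section 5.3 looks like leftover numbering, since Section 6.3 likewise points to 7.2 for consent, which is in 8.2. Section 5 contains no equations, so the reference needs correcting, but it is not evidence of a second dose rule.

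**Conclusion.** The formula is wrong as written. That one FPU is dosed as 0.3 g of carbohydrate follows from the printed lines alone, with no assumption about meal, child or unit. The percentages and fractions of a unit are illustrations that rest on assumed energy factors, carbohydrate contents and ICR values.

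Nothing in the documents shows that so small a dose was meant. The 15-20% quoted from one of the algorithm's two stated sources, and the safety reason for amendment 2, both point the other way, though neither fixes the intended dose and none is proposed here. Because this is the written rule for an insulin dose in children, and its timing is the whole treatment contrast, it must be corrected.

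**What to change.** - State ICR as units of insulin per gram of carbohydrate.
- Put the gram-of-carbohydrate equivalent of one FPU into both the fat/protein line and the total line. The clinical team should set the value in light of amendment 2 and the adult caveat in Section 4.
- Add a worked example for each of the two meal sizes, from its actual macronutrients.
- Change the Visit 2 cross-reference in Section 8.5 from 5.3 to 6.3.
- Check the dose sheets already issued against the corrected formula.

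The cost is two formula lines, one cross-reference, two worked examples and a records check, with no extra patients or procedures.
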